- 2 * Discuss the research design including but not limited to such issues as: probability of group assignment, potential for subject to be randomized to placebo group, use of control subjects, etc.:

Volunteers with a DSM-IV diagnosis of schizophrenia or schizoaffective disorder will be recruited, screened, and allocated in a double-blind manner to either the Nicotine Group or the Placebo Group. All participants will be asked to perform 10 weeks of cognitive remediation training (Posit Science, Duncan, SC), with daily training sessions Monday through Friday. On Mondays and Thursdays, all participants receive a lozenge 20 min prior to the training. In the Nicotine Group, the lozenge will contain 2 or 4 mg of nicotine, depending on smoking status. In the Placebo Group, the lozenge will be a matched placebo.

Outcome measures (OCMs) are assessed on Wednesdays in week 0 (day before training starts), weeks 4, 7 and 10 (after the training session), and week 14 (four weeks after training ends). OCMs are assessed on a non-drug day (Wed) because we are not studying the acute effects of nicotine but nicotine-induced enhancement of longer-term training effects.

- 3 * Describe the relevant prior experience and gaps in current knowledge. Describe any relevant preliminary data:

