
Hypothesis 2a (training progress within nicotine vs. placebo sessions): For those adaptive exercise parameters for which progress is stated at the end of each session, we will compare nicotine - placebo differences on within-session progress, averaged over 20 lozenge-sessions, between treatment groups using a t-test. Power is estimated from the formula⁷⁸ $d = [2(z_a + z_b)2(1-(b-1)r)/bn]$, where d = (difference in average change)/SD(change within 1 session), $b=20$ visits per subject, and other terms are defined as above. For $n=20$ completers per group, we would have power=0.80 at two-sided $\alpha=0.05$ to detect $d=0.51$ (a medium effect size) for $r=0.3$. r is estimated based on each exercise being short and of potentially low reliability. To test Hypothesis 2b (persistence of nicotine-induced improvements beyond the presence of nicotine), we will analyze within-session progress on no-lozenge sessions. If progress made in the nicotine sessions does not persist, we would expect a performance decrement in subsequent no-lozenge sessions (Tue, Fri), whose difficulty levels begin where the previous session left off. If progress made under nicotine does persist, we would expect no decrement and progress comparable to no-lozenge sessions in the placebo group.

To achieve 20 completers per group, we expect having to enroll 25 subjects per group into the training and having to screen approximately 70 subjects in total.

Please note that screening is part of the study protocol. Thus, we expect to consent 70 subjects.

- 2 * Provide the plan for data analysis. Include in the description the types of comparisons that are planned (e.g., comparison of means, comparison of proportions, regressions, analysis of variance, etc.), which is the primary comparison/analysis, and how the analyses proposed will relate to the primary purposes of the study:

Please see above. The sample size calculation is closely related to the planned analyses.

ID: VIEW4E02806052800

Name: v2_Sample Size and Data Analysis

View: v2_Sharing of Results

Sharing of Results

- 1 * Describe whether results (study results or individual subject results, such as results of investigational diagnostic tests, genetic tests, or incidental findings) will be shared with subjects or others (e.g., the subject's primary care physicians) and if so, describe how it will be shared:

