Participants will be asked to perform 10 weeks of computerized cognitive remediation training (Posit Science, Duncan, SC), with daily 80-min training sessions Monday through Friday, usually in the presence of a research assistant. Each cognitive remediation training session will include ~30 min of auditory and ~30 min of visual training exercises by Posit Science, in a counterbalanced manner. Both programs posit that the quality and quantity of processed sensory information form the basis for higher cognitive functions by affecting, e.g., processing speed and the availability of attentional resources. The auditory training consists of six exercises: fast and accurate discrimination of (1) sound frequencies, (2) phonemes and (3) syllables, and recall of syllables, (4) sequences of syllables, (5) multi-element verbal instructions, and (6) details of a narrative. The visual training consists of five exercises designed to (1) improve visual precision, (2) increase capacity to divide visual attention, (3) improve visual memory, (4) expand field of view, and (5) increase visual processing speed. Participants will perform ~15 min of an exercise at a time and complete five exercises per session. The aim is to complete each exercise twice/week and on at least one lozenge-day/week (Mon or Thur). Within these restrictions, we will aim at completing the sound frequency discrimination almost daily.

The programs train the fine-tuned and differentiated processing of sensory input and engage attention, working memory and/or executive processes. To induce the right level of challenge and promote engagement and motivation, task difficulty adjusts continuously to performance to maintain ~85% correct responses (rewarded by auditory and visual feedback). Adjustable parameters are presentation time, interstimulus interval, stimulus similarity, stimulus eccentricity, number of stimuli, and information complexity.

ID: VIEW4E0BC12A9F800
Name: v2_Behavioral Interventions

View: v2_Testing

Testing

You indicated that this study involves neuropsychological or psychophysiological testing.

If you uploaded a separate research protocol document in the 'Research Protocol' page, cite the applicable section and page numbers from that document in the answer boxes below.

- 1 * List all of the tests to be used in the study, including both standardized and non-standardized assessments:

The cognitive status of patients and controls will be assessed by the following tests:

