- The WASI Vocabulary and Matrix Reasoning subtests to assess intellectual competence
- The MATRICS battery
- Visual Acuity Test to test inclusion criterion of normal vision
- Ishihara's Test for Color Deficiency
- Change localization task, to test working memory capacity
- Tests to assess progress on the Posit Science cognitive remediation training exercises
- Cogstate computerized assessment battery

- 2 * Describe procedures related to all testing:

-The WASI subtests are paper and pencil tests and will be administered by an investigator during one of the first three visits (screening, nicotine exposure session prior to lozenge administration, or first outcome measurement session). The setting is a private room, seated at a table.

-The MATRICS battery is a collection of co-normed measures of verbal and visual episodic and working memory, processing speed, problem solving, sustained attention, and social cognition. Most tests are paper and pencil tests done in interaction with the investigator. One subscale involves performing a ~10-min Continuing Performance Task on a computer. The MATRICS battery will be performed every four weeks in each outcome measurement session.

-The Visual Acuity Test consists of reading a sequence of letters with one eye covered at a certain distance from the chart. Performed during screening.

-The Ishihara Test consists of reading green numbers against a red background or vice versa, or finger-tracing a line. Performed during screening.

-The Change localization task is performed at a computer. One or four colored squares are presented for ~200 ms, and after a ~1-s delay, they reappear. The task is to identify the square that has changed color. Performed on outcome measurement days just before and just after the cognitive training (weeks 0 and 10).

-The Posit Science exercises are performed on a computer. Some exercises provide a progress summary of these parameters after each session, which will be recorded. Other exercises provide a separate assessment tool to monitor progress, which will be performed on outcome measurement days every three to four weeks, together with other outcome measurements (see "Study Procedures").

- The Cogstate battery is performed on a computer and comprises tests of processing speed, attention, learning and memory, and higher cognitive functions.

- 3 * Upload relevant testing materials:

Name	Created	Modified Date
Visual Acuity scoring form	12/11/2013 11:01 AM	12/11/2013 11:01 AM

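### If Hypothesis 2a is tested per exercise, b=20 does not fit the training schedule: about 8–10 lozenge-day runs each, so detectable d is 0.54–0.55, not 0.51

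*Combined protocol and SAP*

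**What the plan says.** Sample Size and Data Analysis, item 1, limits the Hypothesis 2a test to certain measures: "For those adaptive exercise parameters for which progress is stated at the end of each session". The outcome is "within-session progress, averaged over 20 lozenge-sessions, between treatment groups using a t-test". The power statement uses b=20 visits per subject, n=20 completers per group, r=0.3, two-sided alpha 0.05 and power 0.80, and gives a detectable d of 0.51. On the correlation it says: "r is estimated based on each exercise being short and of potentially low reliability".

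The count of 20 comes from the design (Justification, Objective, & Research Design, item 2): "On Mondays and Thursdays, all participants receive a lozenge 20 min prior to the training". Two days a week for 10 weeks is 20 sessions.

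Behavioral Intervention, item 1, sets out what happens in a session. There are six auditory and five visual exercises, 11 in all. "Participants will perform ~15 min of an exercise at a time and complete five exercises per session". On frequency: "The aim is to complete each exercise twice/week and on at least one lozenge-day/week (Mon or Thur". One exercise is treated differently: "Within these restrictions, we will aim at completing the sound frequency discrimination almost daily".

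Testing, item 2, confirms that only part of the set can enter this test: "Some exercises provide a progress summary of these parameters after each session, which will be recorded". Neither section names those exercises.

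**The concern.** The power statement takes its two key inputs from different units. The value b=20 counts sessions, while r=0.3 is argued from the properties of one exercise. A participant attends 20 lozenge sessions but does only five of the 11 exercises in each, so a typical exercise is not observed 20 times under the lozenge. If the test is run exercise by exercise, the mean for each participant rests on fewer runs than the formula assumes, and the stated detectable effect is somewhat too small. What is at stake is the accuracy of one published power figure for a mechanistic hypothesis, and clarity about what is being tested.

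**Working it through.** **Inputs.** From the Hypothesis 2a text: n=20 per group, b=20, r=0.3, d=0.51. From the Hypothesis 1a text: z values 1.96 and 0.84. From Behavioral Intervention: 11 exercises, five per session. From the research design: two lozenge days a week for 10 weeks.

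**Step 1: reproduce the plan's figure.** For a mean of b equally correlated measures,

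d = √[2(1.96+0.84)² × f / n], with f = (1+(b−1)r)/b.

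At b=20, f = (1+19×0.3)/20 = 0.335, and d = √(2×7.84×0.335/20) = 0.512, matching the stated 0.51. The formula as it appears in the text has a minus sign before (b−1)r and no legible root, and would give −0.184. Because the version above reproduces the plan's result, I treat the difference as a printing or extraction fault, not an error in the plan.

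**Step 2: count lozenge-day runs.** 5 exercises × 2 days = 10 runs a week, or 100 over 10 weeks. The aim of at least one lozenge-day run a week for all 11 exercises would need 11 a week, so it already slightly exceeds the 10 available. The runs left for the ten exercises other than sound frequency are:

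| Sound frequency on lozenge days | Runs left over 10 weeks | Average per other exercise |
|---|---|---|
| Neither | 100 | 10 |
| One a week | 90 | 9 |
| Both | 80 | 8 |

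Over a full week there are 5×5 = 25 runs. Ten exercises twice each use 20, leaving 5 for sound frequency. If it is in fact run every day, the bottom row applies.

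**Step 3: recompute at n=20 and r=0.3.** Power at d=0.51 is Φ(0.51×√(20/2)/√f − 1.96).

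| b | f | Detectable d | Power at d=0.51 |
|---|---|---|---|
| 20 | 0.335 | 0.512 | 0.796 |
| 10 | 0.370 | 0.539 | 0.755 |
| 9 | 0.378 | 0.544 | 0.747 |
| 8 | 0.3875 | 0.551 | 0.736 |

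The b=20 row shows 0.796 rather than 0.80 only because 0.51 is rounded down from 0.512. At 0.512 the four powers are 0.80, 0.76, 0.75 and 0.74.

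**Step 4: why the change is small, and how it depends on r.** f can be written r + (1−r)/b. At r=0.3, most of it is the 0.3 that extra runs cannot reduce. If r were 0.1 (an assumption), d would go from 0.337 at b=20 to 0.386–0.408 at b=10 to 8. If r were 0.5 (also an assumption), it would go from 0.642 to 0.657–0.664.

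**The case against.** The strongest reply is that the statement is consistent at session level. It averages over lozenge sessions, counts visits, and scales d by the SD of change within one session. Read that way, b=20 is correct. This reading is possible and cannot be excluded, so the point has to stay conditional. It is not the more natural reading: the tested measures are exercise parameters in the plural, r is argued from the single exercise, and no composite is defined. A composite would also need a scaling rule, because the adjustable parameters include such different things as presentation time and number of stimuli.

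Second, 8–10 is an average under aims. One lozenge day a week is a floor, not a cap, and staff could give the exercises that report progress more lozenge-day runs at the expense of others. This stands. A reader might infer that no exercise other than sound frequency can exceed 10 runs; the documents do not say how slots are allocated and do not support that.

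Third, r=0.3 is a judgement without data, and small changes in it matter as much as b. At b=20 and r=0.35, d is 0.548; at r=0.25, b=10, 9 and 8 give 0.505, 0.511 and 0.519. This is true and shows that the discrepancy is small. It does not rescue a figure stated at r=0.3, which should follow from the plan's own r and schedule.

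**Conclusion.** The concern holds on the per-exercise reading. With the plan's own n and r, detectable d for exercises other than sound frequency is about 0.54–0.55 rather than 0.51, 5% to 8% larger (0.539/0.512 to 0.551/0.512). Power at 0.51 is about 0.74–0.76 rather than 0.80.

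This rests on four assumptions: the test is per exercise; five exercises are done in every session; lozenge-day runs are shared about equally among the ten other exercises; and no sessions are missed. Missed sessions would lower the counts further. Sound frequency, planned for nearly every day, could approach 20 runs, but the documents do not say whether it reports progress at the end of a session.

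A reader might go further and infer that Hypothesis 2a cannot be tested, that the group comparison is biased, or that the trial is too small. None of these follows. A mean over 8–10 runs can be formed and compared, both groups follow the same schedule, and the figure of 20 completers per group also serves the MCCB slope analysis, which does not use this b. The effect would still be of the size the plan calls medium.

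**What to change.** In Sample Size and Data Analysis, item 1, list the exercises that report progress at the end of each session and state that the Hypothesis 2a test is made per exercise. Set b to the lozenge-day runs scheduled for each of them, about 8–10, and restate the detectable d as 0.54–0.55 at n=20 per group and r=0.3. Replace the reference to averaging over 20 lozenge sessions with the lozenge-day runs of the exercise concerned.

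If a session-level score was intended, define it explicitly: which exercises enter, how their parameters are put on one scale, and what value of r applies to the composite. b=20 is then correct, and d=0.51 holds only if that r is 0.3.

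The cost is a few sentences. No visits, participants or training time are added, and the training schedule can stay as it is.

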Volunteers who provide Informed Consent will be screened for all Inclusion/Exclusion criteria. SCREENING will include: - Verification of age. - The SCID, to determine the presence/absence of current psychiatric conditions. For most patients, a SCID will have already been obtained and does not need to be repeated. - Medical history targeted at the cardiovascular, neurological, cognitive and other exclusion criteria. - Blood pressure and heart-rate reading. - ECG (12-lead with 3-5 minute rhythm strip). Exclusionary conditions documented on ECG include: Wolfe Parkinson White syndrome Myocardial ischemia and infarction Complete left bundle branch block PR interval <120 ms or >200 ms Prolonged QT interval (corrected) >500 ms Cardiac arrhythmias as defined by PACs >3 per min or PVCs >1 per min - Urine drug test, as a possible indication for substance abuse or dependence (may be repeated at any time during the study if intoxication is suspected) - Alcohol breathalyzer test, as a possible indication for alcohol abuse or dependence (may be repeated at any time during the study if intoxication is suspected) - Urine pregnancy test for females (also performed at the beginning of the cognitive training phase, and every two weeks thereafter) - Targeted questions about smoking history and motivation to stop smoking - Breath CO reading, as an indicator of smoking status and frequency - Listing of all currently taken medication - Vision test - The Addiction Severity Index - Drug and Alcohol Use subscale as an indicator for substance abuse or dependence. - The Wechsler Abbreviated Scale of Intelligence (WASI), as an indicator for possible mental retardation. Volunteers who pass the screening will be randomized to either the nicotine group or the placebo group. Randomization will be performed by the MPRC's biostatistician, [name], upon receiving a randomization request from the research assistant coordinating the study or a study investigator. Participants are then scheduled for a first NICOTINE EXPOSURE SESSION. In this session, participants will consume a nicotine lozenge (2 mg for non-smokers, 4 mg for smokers) if they have been randomized to the nicotine group and a placebo lozenge if they have been randomized to the placebo group. The number of smokers will be counterbalanced between the nicotine and placebo group. Participants will be instructed not to eat or drink within 15 min prior to or while consuming the lozenge. Participants are asked to report any adverse effects as soon as noted and to rate their subjective state immediately before the lozenge and every 30 min thereafter (see Side-Effects Checklist under "Additional Documents"). At this time, an investigator will also take their blood pressure and heart rate. The adverse effects of nicotine develop rapid tolerance. If any adverse effects are observed that are greater than "mild" and were not present pre-lozenge, the participant will undergo another lozenge exposure session on a separate day before starting the study. This may be repeated up to 4 times. Once both the participant and the investigator judge that any untoward effects of the lozenge are mild and tolerable and will not interfere with the cognitive training, the first outcome measurement session is scheduled, and the daily training sessions will commence the day after. A smoker who cannot tolerate the 4-mg lozenge may be dosed with a 2-mg lozenge in the cognitive training phase (the study would be single-blind for this subject). A participant who cannot tolerate the 2-mg lozenge even after repeated attempts will be excluded from the study. Participants who with the 2 mg lozenge display a rise in blood pressure by >20 mm Hg relative to pre-lozenge, a rise in HR to >120, or vomiting, will also be excluded from the study. OUTCOME MEASUREMENTS will be performed before the training begins, and approximately every 4 weeks after that until 4 weeks after the training ends. During the training phase, the outcome measurements will be performed AFTER completion of the daily cognitive training session. We will always schedule at least 1 hour between training and the outcome measurement, during which the participant can rest or have lunch. Outcome assessments are: a) The MATRICS Consensus Cognitive Battery (MCCB), an FDA-approved assessment tool for trials of cognition-enhancing treatments in PSZ. The battery measures 7 domains: speed of processing, attention/vigilance, working memory (verbal, nonverbal), verbal learning, reasoning, problem solving, and social cognition. b) The progression in training exercise parameters since the last outcome measurement time point (see below). c) Symptom assessments: the Brief Psychiatric Rating Scale, Scale for Assessment of Negative Symptoms, and Calgary Depression Scale. d) The state version of the State-Trait Anxiety Inventory. e) The Cogstate computerized assessment battery. Further outcome measures taken only pre- and post-training (week 0 and 10): a) Working Memory capacity (K) derived from a computerized change localization task. Two to four colored squares are shown for 100 ms. After a delay, they reappear and the task is to click on the one square that has changed color. b) The UCSD Performance-Based Skills Assessment, measuring ability to perform real-life tasks by standardized role-play. c) Quality of Life Scale, measuring functional outcome and quality of life in PSZ. d) The trait version of the State-Trait Anxiety Inventory. e) The Cognitive Assessment Interview (CAI), a brief interview-based measure of daily life cognitive functioning, administered to both the PSZ and a close relative or caretaker. The CAI was developed based on two longer scales and assesses 10 items related to working memory, attention/vigilance, learning/memory, problem solving, processing speed, and social cognition, with little or no repetition effects. f) Questionnaire asking each participant to guess their treatment group (nicotine or placebo; post-training only). g) A 5-ml venous blood sample will be taken, centrifuged, and frozen. At the completion of the study, the samples will be analyzed for TNF alpha, and potentially other inflammatory markers, to test whether repeated nicotine exposure may have anti-inflammatory effects that may be related to any effects on cognitive outcome measures. If a participant declines to have their blood drawn but are otherwise eligible for the study, they may participate without the blood draws. COGNITIVE REMEDIATION TRAINING PROCEDURE Prior to each daily training session, participants will complete a brief checklist about their caffeine and cigarette consumption today (how much/how many), when they last smoked/drank a caffeinated beverage, how many hours of sleep they got the previous night, when they last drank alcohol and how much. Prior to each session, smokers also provide a CO breathalyzer reading. Each training session will include ~30 min of auditory and ~30 min of visual training exercises by Posit Science, in a counterbalanced manner. The auditory training consists of six exercises: fast and accurate discrimination of (1) sound frequencies, (2) phonemes and (3) syllables, and recall of syllables, (4) sequences of syllables, (5) multi-element verbal instructions, and (6) details of a narrative. The visual training consists of five exercises designed to (1) improve visual precision, (2) increase capacity to divide visual attention, (3) improve visual memory, (4) expand field of view, and (5) increase visual processing speed. The programs train the fine-tuned and differentiated processing of sensory input and engage attention, working memory and/or executive processes. To induce the right level of challenge and promote engagement and motivation, task difficulty adjusts continuously to user performance to maintain ~85% correct responses (which are rewarded by auditory and visual feedback). Adjustable parameters include presentation time, interstimulus interval, physical similarity between stimuli, stimulus eccentricity, number of stimuli, and information complexity. Some exercises provide a progress summary of these parameters after each session. These values will be recorded on all training days. Other exercises provide a separate assessment tool to monitor progress. These assessments will be performed every 4 weeks with other outcome measurements. Every Monday and Thursday, a nicotine or placebo lozenge, encapsulated in gelatin, will be administered 20 minutes prior to the beginning of the training. Nicotine lozenges are mint-flavored "mini" lozenges, placebo lozenges are size-matched breath mints. Smokers in the Nicotine Group will receive a 4-mg lozenge. Plasma concentrations after this dose resemble the "nicotine boost" typically seen in dependent smokers by smoking a single cigarette (~1 ng/ml). Non-smokers in the Nicotine Group will receive a 2-mg lozenge because 4 mg in nicotine-naïve individuals would likely result in low tolerability. Participants will be instructed not to eat or drink within 15 min prior to or while consuming their lozenge. Participants may perform the training sessions at the Maryland Psychiatric Research Center (MPRC), or, in a separate room, at their day program or inpatient unit if applicable (a research associate would visit daily with laptop, lozenge or assessment instruments). The lozenge would be administered by a local nurse or other medical professional if possible, else these sessions would be performed at the MPRC. Participants who are unable to come to the MPRC or day program to complete the training (e.g., because they work or live too far away) may perform the exercises at home if they have internet access and their clinician or study staff considers them capable of doing so reliably. The CO measurement would be omitted on home-training days, and participants would be given the questionnaire about how much they slept and how much caffeine or alcohol they consumed to complete by themselves at home. On the two weekly lozenge days, they would be scheduled to perform the training at the MPRC. Under select circumstances, when the patient is unable to come to the MPRC on those days, too, they would be instructed to take the lozenge at home, following doctor's orders. A study team member would call them at home and

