- Coughing. This is a relatively likely but non-serious risk.
- Diaphoresis. This is a relatively likely but non-serious risk.
- Dizziness. This is a moderately serious but relatively unlikely risk.
- Dry mouth. This is a relatively unlikely and minor risk.

- Headache. This is a moderately likely but relatively minor risk.
- Nausea. This is a moderately likely but relatively minor risk.
- Vomiting. This is a moderately serious but relatively unlikely risk.
- Palpitations. This is a moderately likely but minor risk.
- Injury to mouth, teeth or dental work from consuming lozenges. This is a moderately serious but unlikely risk. This side effect is particularly unlikely in the present study because participants only consume 2 lozenges/week, as opposed to several/day when used for smoking cessation.
- Mild jaw muscle ache. This is an unlikely and minor risk. This side effect is particularly unlikely in the present study because participants only consume 2 lozenges/week, as opposed to several/day when used for smoking cessation.
- Restlessness. This is a relatively unlikely and minor risk.
- Sleepiness. This is a relatively unlikely and minor risk.
- Sore mouth or throat. This is a moderately likely but relatively minor risk.
- Temporary mood changes. This is a relatively unlikely and minor risk.

Risk minimization for all of the above risks:

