All effects are temporary and will dissipate spontaneously with the metabolism of nicotine (half-life: 2.3 hours for the lozenge). Only individuals who meet certain medical history criteria will be admitted into the study. Participants will consume at least one lozenge before the training program starts. Subjective and cardiovascular (blood pressure, heart rate) effects of the lozenge will be monitored for 3 hours. This will identify subjects prone to experiencing any greater than expected untoward effects, such as a rise in blood pressure by >20 mm Hg, a rise in HR to >120, or vomiting. Such subjects would be excluded from the trial. Participants with side effects less severe than the above, but which they perceive as disruptive, will receive a further lozenge on a separate day before the start of the training intervention. Due to rapid tolerance to the adverse effects of nicotine, this pre-exposure will reduce unpleasant effects of nicotine during training. Furthermore, participants are asked not to chew the lozenge or swallow it whole. The lozenges dissolve over 10 min, thus enforcing a relatively slow rise in nicotine blood levels.

- Another risk is related to nicotine being an addictive substance. Nicotine addiction would be a serious but very unlikely risk. The likelihood of any reinforcing properties of the nicotine lozenge leading to abuse liability is very low. The abuse liability of a drug depends on the kinetics of drug delivery, such that reinforcing properties are greater for delivery routes associated with faster absorption. Nicotine plasma levels peak approximately 1 hour following administration of a nicotine polacrilex lozenge, and the protracted absorption of nicotine has been shown to not produce subjectively reinforcing effects. There is however a concern that nicotine lozenges may trigger relapse in former regular smokers because the subjective effects, even if not reinforcing in themselves, may be associated with dependent cigarette smoking and dependence-related effects of cigarette-derived nicotine. Thus, lozenge-derived nicotine may act as a priming cue. Risk minimization: Former smokers will not be included in this study.

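### The stop rules for the smokers' 4 mg test lozenge differ: Research Related Risks excludes for a blood pressure rise, high heart rate or vomiting at any dose, while Study Procedures does so only at 2 mg

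*Combined protocol and SAP*

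**What the plan says.** Study Procedures, item 1, describes a lozenge exposure session after randomization. In the nicotine group smokers take 4 mg and non-smokers 2 mg; the placebo group takes a placebo lozenge. Blood pressure and heart rate are taken before the lozenge and every 30 minutes afterwards. The section then sets these rules:

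- After a new adverse effect greater than mild, "the participant will undergo another lozenge exposure session on a separate day before starting the study". On further repeats: "This may be repeated up to 4 times".
- "A smoker who cannot tolerate the 4-mg lozenge may be dosed with a 2-mg lozenge in the cognitive training phase". The plan adds that "the study would be single-blind for this subject".
- Anyone who still cannot tolerate 2 mg after repeated attempts is excluded.
- The hard stop carries a dose: "Participants who with the 2 mg lozenge display a rise in blood pressure by >20 mm Hg relative to pre-lozenge", or whose heart rate rises above 120, or who vomit, are excluded.
- Training waits for a joint judgement: "Once both the participant and the investigator judge that any untoward effects of the lozenge are mild and tolerable".

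Research Related Risks, item 1 a), describes the same pre-training exposure. It gives the same three reactions as examples of greater than expected effects of the lozenge, states no dose, and concludes: "Such subjects would be excluded from the trial". It keeps a further lozenge for side effects that are less severe than these but that the participant finds disruptive.

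**The concern.** Both sections tell staff what to do after a bad reaction to the test lozenge, and for a smoker on 4 mg they do not tell them the same thing. One section excludes. The other, read alone, sets its hard stops only at the lower dose and continues with repeat exposure or a lower dose.

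What is at stake is the clarity of a safety rule in a study that the application itself rates as greater than minimal risk. If Study Procedures is the working rule, Research Related Risks describes a stricter safeguard than the one applied at 4 mg. If Research Related Risks is the working rule, smokers whom Study Procedures would keep are removed. In addition, Study Procedures places the step-down in the training phase and does not expressly require a monitored 2 mg session first. Training lozenges may be given at day programs and, in select circumstances, taken at home.

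**Working it through.** No arithmetic applies, so the check sets the two sections side by side. The rows are for the nicotine group.

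| Reaction to the test lozenge | Study Procedures, item 1 | Research Related Risks, item 1 a) |
|---|---|---|
| Any of the three reactions at 2 mg | Exclude | Exclude |
| Vomiting at 4 mg | If rated more than mild, repeat session; step-down to 2 mg if 4 mg is not tolerated | Exclude |
| Blood pressure rise >20 mm Hg or heart rate >120 at 4 mg, no symptoms | No express rule | Exclude |

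**Step 1, vomiting at 4 mg.** The list of adverse events in Research Related Risks says: "Vomiting. This is a moderately serious but relatively unlikely risk". That supports rating it above mild, but only indirectly. The entry grades the seriousness of a risk, while the mild threshold in Study Procedures presumably refers to the Side-Effects Checklist, whose content is not in the documents. If vomiting is rated above mild, Study Procedures requires another session and Research Related Risks excludes. If it were rated mild, Study Procedures would not require the repeat, but it still would not exclude. The two sections differ under either rating.

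**Step 2, symptom-free blood pressure or heart rate rise at 4 mg.** These readings will exist, because the session collects them. Study Procedures names them as triggers only with the 2 mg lozenge. Two readings are open:

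- The rise counts as an effect greater than mild, or as failure to tolerate 4 mg. Repeat exposure or step-down then follows, against exclusion in Research Related Risks.
- The rise does not count. Study Procedures then has no rule for it.

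Neither reading produces the exclusion that Research Related Risks states.

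**Step 3, which section governs.** Withdrawal of Participants, item 1, sends the reader to Study Procedures for stop criteria, so that section probably governs and Research Related Risks is too broad. The section on resources, item 3, implies that some first-exposure effects disqualify a participant but does not say which. Item 4 there says that a Study Manual will cover adverse-event procedures. The manual is not among the documents, so the rule that staff would follow is unknown.

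**Step 4, how many.** The documents give no reaction rate at 4 mg and no expected number of smokers. No count can be derived. The risk list calls vomiting relatively unlikely, which suggests few cases.

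**The case against.** The strongest reply is that the plan already says where its stop rule is. Withdrawal of Participants points to Study Procedures, which reads as a ladder from repeat exposure, through 4 mg to 2 mg, to exclusion at 2 mg. Research Related Risks introduces the three reactions as examples and can be taken as a summary that lacks one qualifier. The application states that there is no separate protocol, so both sections lie in one submission and the IRB had both. This stands as far as it goes: Study Procedures probably governs. But the summary states a definite consequence and its own tier for re-exposure, and correcting it would still leave Study Procedures without an express blood pressure or heart rate rule at 4 mg.

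A second reply is that the gate before training already covers such readings, since they are plausibly untoward effects that must be judged mild and tolerable. That is a fair reading. It makes the outcome a matter of judgement where the same readings at 2 mg are a fixed stop.

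A third reply is that the hazard is small. This stands. A nurse must be on site and a physician on call for the first lozenge, and for repeat exposures after side effects that did not disqualify the participant. Participants may also be withdrawn if nicotine effects make continuing unsafe.

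A fourth reply concerns remedies. A flat ban on further 4 mg exposure would override the plan's stated reason for repeating the lozenge, which is rapid tolerance, and blinded staff could not apply it to nicotine recipients alone. Both objections stand, and the fix allows for them.

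**Conclusion.** The inconsistency is real and should be corrected. It is confined to smokers at the 4 mg test lozenge. For vomiting, the two sections give different dispositions. For a symptom-free blood pressure or heart rate rise, Research Related Risks excludes and Study Procedures has no express rule. At 2 mg the sections agree. The conclusion assumes that Research Related Risks means what it literally says in naming no dose. The finding that Study Procedures sends vomiting at 4 mg to a repeat session further assumes that vomiting is rated above mild.

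A reader might infer three stronger things that the documents do not support:

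- *That the sections contradict each other outright on all three reactions.* For blood pressure and heart rate, Study Procedures is not explicit at 4 mg, so a flat contradiction depends on how a bare reading is classed.
- *That smokers are left unprotected.* The supervision, the gate before training and the power to withdraw participants all remain.
- *That the treatment comparison is biased.* The test lozenge follows randomization, so the rule chosen could bear mainly on exclusions in the nicotine group. Without reaction rates or a number of smokers, nothing about arm balance can be shown, and no effect on the analysis is claimed.

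**What to change.** Three changes:

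1. In Research Related Risks, limit the exclusion to reactions with the 2 mg lozenge and refer to Study Procedures for what happens at 4 mg.
2. In Study Procedures, add a rule for a smoker who has any of the three reactions at the smokers' test level. That person may not start training at that level unless a repeat monitored session is free of all three. Otherwise the smoker steps down to 2 mg and has a monitored 2 mg session before training, at which the existing 2 mg exclusion rule applies. Repeat exposure at 4 mg, and its tolerance rationale, is thereby kept.
3. Apply the rule by smoking status in both arms, so that staff who do not know the allocation can follow it. Placebo-group smokers would go through the same steps with placebo lozenges.

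The cost is a few sentences of text and an occasional extra monitored session. The 2 mg session should be planned within the up to 4 repeats already allowed. Because the plan treats a stepped-down smoker as single-blind, there may also be a few more single-blind participants.
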